## SYNOPSIS

Protocol Title:	A Single-Center, Phase 2a, Randomized, Double-Masked, Clinical Study to Assess the Safety, Tolerability, and Pharmacodynamic Activity of ADX-102 Ophthalmic Solution in Subjects with Dry Eye Syndrome
Protocol Number:	ADX-102-DES-007
Study Drug:	1) ADX-102 Ophthalmic Solution (0.5%) 2) ADX-102 Ophthalmic Solution (0.1%) 3) ADX-102 Ophthalmic Lipid Solution (0.5%)
Study Phase:	2a
Study Objective:	The objective of this study is to evaluate the safety, tolerability, and pharmacodynamic activity of ADX-102 Ophthalmic Solutions and ADX-102 Ophthalmic Lipid Solution in subjects with dry eye syndrome.
Overall Study Design	
Structure:	Single-center, double-masked, randomized study
Duration:	An individual subject's participation is estimated to be approximately 4 weeks (28 days).
Dosage/Dose Regimen:	Subjects eligible to be randomized will receive one of the following treatments to be administered bilaterally four times daily (QID) for 28 days (from Visit 1 to Visit 3). 1) ADX-102 Ophthalmic Solution (0.5%) 2) ADX-102 Ophthalmic Solution (0.1%) 3) ADX-102 Ophthalmic Lipid Solution (0.5%)
Summary of Visit Schedule:	3 visits over the course of approximately 4 weeks 

• Visit 1 = Day 1, Screening and Enrollment

• Visit 2 = Day 8 ± 1, 1-Week Follow-Up

• Visit 3 = Day 29 ± 2, 4-Week Follow-Up

Measures Taken to Reduce Bias:	This is a randomized treatment assignment, double-masked study.
Study Population Characteristics	
Number of Subjects:	Approximately 60 subjects will be screened to enroll 45 subjects (15 per treatment arm).
Condition/Disease:	Dry Eye Syndrome (DES)

Inclusion Criteria:	Subjects must: 
 
1. Be at least 18 years of age of either gender and any race;
 
2. Provide written informed consent and sign the Health Information Portability and Accountability Act (HIPAA) form;
 
3. Have a reported history of dry eye for at least [REDACTED] prior to Visit 1;
 
4. Have a history of use or desire to use eye drops for dry eye symptoms within [REDACTED] of Visit 1;
 
5. Report a score of [REDACTED] on the Ora Calibra® Ocular Discomfort & 4-symptom questionnaire in at least one symptom at Visit 1;
 
6. Have a Schirmer's Test score of [REDACTED] at Visit 1;
 
7. Have a tear film break-up time (TFBUT©) [REDACTED] at Visit 1;
 
8. Have a corneal fluorescein staining score of [REDACTED] in at least one region (e.g. inferior, superior, or central) at Visit 1;
 
9. Have a sum corneal fluorescein staining score of [REDACTED], based on the sum of the inferior, superior, and central regions, at Visit 1;
 
10. Have a total lissamine green conjunctival score of [REDACTED], based on the sum of the temporal and nasal regions at Visit 1;
 
11. Have at least one eye satisfy all criteria for 6, 7, 8, 9, and 10 above.
 

Exclusion Criteria:	Subjects must not: 
 
1. Have any clinically significant slit lamp findings at Visit 1 that may include active blepharitis, meibomian gland dysfunction (MGD), lid margin inflammation, or active ocular allergies that require therapeutic treatment, and/or in the opinion of the investigator may interfere with study parameters;
 

	

2. Be diagnosed with an ongoing ocular infection (bacterial, viral, or fungal), or active ocular inflammation at Visit 1;

3. Have worn contact lenses within 7 days of Visit 1 or anticipate using contact lenses during the study;

4. Have used any eye drops within 2 hours of Visit 1;

5. Have previously had laser-assisted in situ keratomileusis (LASIK) surgery within the last 12 months;

6. Have used cyclosporine 0.05% or lifitigrast 5.0% ophthalmic solution within 45 days of Visit 1;

7. Have any planned ocular and/or lid surgeries over the study period or any ocular surgery within the last 6 months;

8. Be using or anticipate using temporary punctal plugs during the study that have not been stable within 30 days of Visit 1;

9. Be currently taking any topical ophthalmic prescription (including medications for glaucoma) or over-the-counter (OTC) solutions, artificial tears, gels or scrubs, and cannot discontinue these medications for the duration of the trial (excluding medications allowed for the conduct of the study);

10. Have corrected visual acuity greater than or equal to logarithm of the minimum angle of resolution (logMAR) + 0.7 as assessed by Early Treatment of Diabetic Retinopathy Study (ETDRS) scale in both eyes at Visit 1;

11. Be a woman who is pregnant, nursing, or planning a pregnancy;

12. Be unwilling to submit a urine pregnancy test at Visit 1 and Visit 3 (or early termination visit) if of childbearing potential. Non-childbearing potential is defined as a woman who is permanently sterilized (e.g., has had a hysterectomy or tubal ligation), or is post-menopausal (without menses for 12 consecutive months);

--	---

	
13. Be a man or woman of childbearing potential who is not using an acceptable means of birth control; acceptable methods of contraception include: hormonal – oral, implantable, injectable, or transdermal contraceptives; mechanical – spermicide in conjunction with a barrier such as a diaphragm or condom; intrauterine device (IUD); or surgical sterilization of partner. For non-sexually active males or females, abstinence may be regarded as an adequate method of birth control; however, if the subject becomes sexually active during the study, he/she must agree to use adequate birth control as defined above for the remainder of the study;
 
14. Have a known allergy and/or sensitivity to the test article or its components;
 
15. Have a condition or be in a situation which the investigator feels may put the subject at significant risk, may confound the study results, or may interfere significantly with the subject's participation in the study;
 
16. Be currently enrolled in an investigational drug or device study or have used an investigational drug or device within 30 days of Visit 1;
 
17. Have previously used ADX-102 ophthalmic solution;
 
18. Be currently using any medication known to cause ocular drying that is not used on a stable dosing regimen for at least 30 days prior to Visit 1;
 
19. Be unable or unwilling to follow instructions, including participation in all study assessments and visits.

Study Formulations:	
 
• ADX-102 Ophthalmic Solution (0.5%)
 
• ADX-102 Ophthalmic Solution (0.1%)
 
• ADX-102 Ophthalmic Lipid Solution (0.5%)
 

[REDACTED]

[REDACTED]

[REDACTED]

[REDACTED]

[REDACTED]

[REDACTED]

[REDACTED]

[REDACTED]

Primary Efficacy Analyses:

There are no primary endpoints in this Phase 2a study.

Secondary Efficacy Analyses:

There are no secondary endpoints in this Phase 2a study.

Safety Variables:

Adverse events (AEs) will be coded using the MedDRA dictionary. Frequencies and percentages of subjects with treatment-emergent adverse events (TEAEs), serious TEAEs, and TEAEs causing premature discontinuation will be provided by treatment group. An AE is treatment emergent if it occurs or worsens after the first dose of study treatment. Furthermore, frequencies will be given of subjects with TEAEs by system organ class, by system organ class and preferred term, by system organ class, preferred term and maximal severity, by system organ class, preferred term and strongest relationship, and by system organ class, preferred term, maximal severity, and strongest relationship. Separate summaries will be performed for ocular and non-ocular AEs.

Other safety endpoints including visual acuity, slit-lamp biomicroscopy, undilated fundoscopy, and intraocular pressure will be summarized by treatment group and visit using descriptive statistics. Changes or shifts from baseline will also be summarized where appropriate. For assessments performed by eye, study eye and fellow eye will be summarized separately.

[REDACTED]

[REDACTED]

[REDACTED]

[REDACTED]

[REDACTED]

[REDACTED]

[REDACTED]

---

**Summary of Known and Potential Risks and Benefits to Human Subjects**

Refer to Investigator's Brochure.

## LIST OF ABBREVIATIONS

AE	adverse event
BCVA	best-corrected visual acuity
CFR	Code of Federal Regulations
CRF	case report form
DES	Dry Eye Syndrome
DHHS	Department of Health and Human Services
eCRF	electronic case report form
EKG	Electrocardiograph
ERC	ethical review committee
ETDRS	Early Treatment of Diabetic Retinopathy Study
FDA	Food and Drug Administration
GCP	Good Clinical Practice
HIPAA	Health Information Portability and Accountability Act
ICF	informed consent form
ICH	International Conference on Harmonization
IEC	Independent Ethics Committee
IND	investigational new drug application
IOP	intraocular pressure
IRB	institutional/independent review board
ITT	intent-to-treat
IUD	Intra-uterine device
IWRS	interactive web response system
LASIK	laser in situ keratomileusis
LOCF	last observation carried forward
LPS	lipopolysaccharide
logMAR	logarithm of the minimum angle of resolution
MDA	Malondialdehyde; malonaldehyde
MedDRA	Medical Dictionary for Regulatory Activities
MGD	meibomian gland dysfunction
mL	Milliliter
mm	Millimeter
µg	microgram
µL	microliter
µm	Micrometer
mmHg	millimeters of mercury
OD	right eye
OS	left eye
[REDACTED]	[REDACTED]
OU	both eyes
OTC	over-the-counter
PP	per protocol
QID	four times a day
SAE	serious adverse event

[REDACTED]  
TEAEs

[REDACTED]  
treatment emergent adverse events  
VA

## 1 INTRODUCTION

A 5x5 grid of 25 horizontal black bars of varying lengths. The bars are arranged in five rows and five columns. The lengths of the bars are as follows: Row 1: 100%, 100%, 100%, 100%, 100% (all 100%); Row 2: 100%, 100%, 100%, 100%, 100% (all 100%); Row 3: 100%, 100%, 100%, 100%, 100% (all 100%); Row 4: 100%, 100%, 100%, 100%, 100% (all 100%); Row 5: 100%, 100%, 100%, 100%, 100% (all 100%).

A horizontal bar chart with 15 categories on the y-axis and a count of samples on the x-axis (0 to 1000). The bars are black. The distribution is highly skewed, with most categories having between 500 and 1000 samples, and a few categories having significantly fewer samples.

Category	Approximate Sample Count
1	980
2	980
3	650
4	980
5	980
6	150
7	980
8	980
9	980
10	150
11	980
12	980
13	980
14	980
15	980
16	250
17	980
18	980
19	980
20	100

## 2 CLINICAL STUDIES OF ADX-102 OPHTHALMIC SOLUTION

Term	Percentage (%)
GDP	98
Inflation	98
Interest rates	98
Central bank	98
Monetary policy	98
Quantitative easing	98
Inflation targeting	98
Interest rate hike	98
Interest rate cut	98
Interest rate parity	98
Nominal interest rate	98
Real interest rate	98
Nominal GDP	98
Real GDP	98
Nominal exchange rate	75
Real exchange rate	65
Nominal income	98
Real income	98

A large grid of black bars on a white background, representing a data visualization or a redacted document. The grid consists of approximately 20 horizontal rows and 30 vertical columns. The bars are solid black and vary in length, creating a pattern of horizontal and vertical lines. Some bars are very long, while others are shorter, often ending in a vertical line. The overall effect is a high-contrast, abstract graphic.

### 3 STUDY OBJECTIVES

[figure not shown]
The objective of this study is to evaluate the safety, tolerability and pharmacodynamic activity of ADX-102 Ophthalmic Solutions (0.5% and 0.1%) and ADX-102 Ophthalmic Lipid Solution (0.5%) in subjects with dry eye.

### CLINICAL HYPOTHESIS

[REDACTED]

### 4 DESIGN

This is a Phase 2a, single-center, randomized, double-masked study designed to evaluate the safety, tolerability and pharmacodynamic activity of ADX-102 Ophthalmic Solution (0.5%), ADX-102 Ophthalmic Solution (0.1%), and ADX-102 Ophthalmic Lipid Solution (0.5%) in subjects with dry eye. Approximately 45 male and female subjects at least 18 years of age with a subject-reported history of dry eye in both eyes and meeting all other study eligibility criteria will be randomized to receive treatment ADX-102 Ophthalmic Solution (0.5%), ADX-102 Ophthalmic Solution (0.1%), or ADX-102 Ophthalmic Lipid Solution (0.5%) in a 1:1:1 ratio (approximately 15 subjects in each treatment group).

Subjects who terminate early during the treatment period will be asked to complete safety assessments (as listed in [Appendix 1](#)) prior to commencement of any alternative dry eye therapy (if at all possible). Subjects who are terminated early from the study will not be replaced.

## 5 STUDY POPULATION

### 5.1 Number of Subjects

It is estimated that approximately 60 subjects will be screened to enroll approximately 45 randomized subjects (15 in each arm). Subjects will be randomized in a 1:1:1 ratio of ADX-102 Ophthalmic Solution (0.5%) to ADX-102 Ophthalmic Solution (0.1%) to ADX-102 Ophthalmic Lipid Solution (0.5%).

## 5.2 Study Population Characteristics

All subjects must be at least 18 years of age, of either gender, and of any race, and must meet all inclusion criteria and none of the exclusion criteria.

## 5.3 Inclusion Criteria

### Subjects must:

1. Be at least 18 years of age of either gender and any race;
2. Provide written informed consent and sign the Health Information Portability and Accountability Act (HIPAA) form;
3. Have a reported history of dry eye for at least [REDACTED] prior to Visit 1;
4. Have a history of use or desire to use eye drops for dry eye symptoms within [REDACTED] of Visit 1;
5. Report a score of [REDACTED] on the Ora Calibra® Ocular Discomfort & 4-symptom questionnaire in at least one symptom at Visit 1;
6. Have a Schirmer's Test score of [REDACTED] at Visit 1;
7. Have a tear film break-up time (TFBUT©) [REDACTED] at Visit 1;
8. Have a corneal fluorescein staining score of [REDACTED] in at least one region (e.g. inferior, superior, or central) at Visit 1;
9. Have a sum corneal fluorescein staining score of [REDACTED] based on the sum of the inferior, superior, and central regions, at Visit 1;
10. Have a total lissamine green conjunctival score of [REDACTED] based on the sum of the temporal and nasal regions at Visit 1;
11. Have at least one eye satisfy all criteria for 6, 7, 8, 9, and 10 above.

## 5.4 Exclusion Criteria

### Subjects must not:

1. Have any clinically significant slit lamp findings at Visit 1 that may include active blepharitis, meibomian gland dysfunction (MGD), lid margin inflammation, or active ocular allergies that require therapeutic treatment, and/or in the opinion of the investigator may interfere with study parameters;

2. Be diagnosed with an ongoing ocular infection (bacterial, viral, or fungal), or active ocular inflammation at Visit 1;
3. Have worn contact lenses within 7 days of Visit 1 or anticipate using contact lenses during the study;
4. Have used any eye drops within 2 hours of Visit 1;
5. Have previously had laser-assisted in situ keratomileusis (LASIK) surgery within the last 12 months;
6. Have used cyclosporine 0.05% or lifitigrast 5.0% ophthalmic solution within 45 days of Visit 1;
7. Have any planned ocular and/or lid surgeries over the study period or any ocular surgery within the last 6 months;
8. Be using or anticipate using temporary punctal plugs during the study that have not been stable within 30 days of Visit 1;
9. Be currently taking any topical ophthalmic prescription (including medications for glaucoma) or over-the-counter (OTC) solutions, artificial tears, gels or scrubs, and cannot discontinue these medications for the duration of the trial (excluding medications allowed for the conduct of the study);
10. Have corrected visual acuity greater than or equal to logarithm of the minimum angle of resolution (logMAR) + 0.7 as assessed by Early Treatment of Diabetic Retinopathy Study (ETDRS) scale in both eyes at Visit 1;
11. Be a woman who is pregnant, nursing, or planning a pregnancy;
12. Be unwilling to submit a urine pregnancy test at Visit 1 and Visit 3 (or early termination visit) if of childbearing potential. Non-childbearing potential is defined as a woman who is permanently sterilized (e.g., has had a hysterectomy or tubal ligation), or is post-menopausal (without menses for 12 consecutive months);
13. Be a man or woman of childbearing potential who is not using an acceptable means of birth control; acceptable methods of contraception include: hormonal – oral, implantable, injectable, or transdermal contraceptives; mechanical – spermicide in conjunction with a barrier such as a diaphragm or condom; intrauterine device (IUD); or surgical sterilization of partner. For non-sexually active males or females, abstinence may be regarded as an adequate method of birth control; however, if the subject becomes sexually active during the study, he/she

must agree to use adequate birth control as defined above for the remainder of the study;

14. Have a known allergy and/or sensitivity to the test article or its components;
15. Have a condition or be in a situation which the investigator feels may put the subject at significant risk, may confound the study results, or may interfere significantly with the subject's participation in the study;
16. Be currently enrolled in an investigational drug or device study or have used an investigational drug or device within 30 days of Visit 1;
17. Have previously used ADX-102 ophthalmic solution;
18. Be currently using any medication known to cause ocular drying that is not used on a stable dosing regimen for at least 30 days prior to Visit 1;
19. Be unable or unwilling to follow instructions, including participation in all study assessments and visits.

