### 8.1.2 Informed Consent

Prior to a subject's participation in the trial (i.e., prior to changes in a subject's medical treatment and/or prior to study related procedures), the study will be discussed with each subject, and subjects wishing to participate must give written informed consent using an informed consent form (ICF). The ICF must be the most recent version that has received approval/favorable review by a properly constituted Institutional Review Board (IRB).

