### 8.1.3 Washout Intervals

Prohibited medications, treatments, and activities are outlined in the exclusion criteria (Section 5.4).

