### **8.4.2 Unscheduled Visits**

These visits may be performed in order to ensure subject safety. All procedures performed at an unscheduled visit will be recorded in the source documents and on the Unscheduled Visit eCRF pages. Any procedure indicated in the eCRF that is not performed should be indicated as "Not done."

Evaluations that may be conducted at an Unscheduled Visit include:

- Slit-lamp Biomicroscopy;
- Visual Acuity;
- Intraocular Pressure;
- Urine Pregnancy Test;
- Undilated Fundoscopy;
- Assessment of Adverse Events;
- Assessment of concurrent medications and/or treatments; and
- Any other assessments needed in the judgment of the investigator.

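### Exclusion 9 does not bar a glaucoma-drop user judged able to stop, and the next scheduled IOP reading is 26 to 30 days later

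*Protocol*

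**What the plan says.** **Eligibility.** Protocol Section 5.4, exclusion 9, covers a subject found to "Be currently taking any topical ophthalmic prescription (including medications for glaucoma"; over-the-counter drops, gels and scrubs are also listed. It joins this with 'and' to a second condition, that the subject "cannot discontinue these medications for the duration of the trial". The synopsis has the same wording. No other visible criterion mentions glaucoma or IOP. Exclusion 15 lets the investigator refuse anyone whose condition or situation "may put the subject at significant risk, may confound the study results".

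**Washout.** Section 8.1.3 sets no interval of its own: "Prohibited medications, treatments, and activities are outlined in the exclusion criteria". Within Section 5.4, exclusion 4 applies to all drops ("Have used any eye drops within 2 hours of Visit 1"). The longer interval in exclusion 6 ("ophthalmic solution within 45 days of Visit 1") covers cyclosporine and lifitegrast only.

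**Timing of stopping.** Section 8.1.2 requires consent "prior to changes in a subject's medical treatment". Section 8.3.1 and SAP Section 3.2 place consent, the baseline IOP reading and randomization all at Visit 1.

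**Use during the study.** Section 8.2.1 refers to the exclusion criteria for disallowed medication, and SAP Section 9 lists use of prohibited medication as a category of protocol deviation.

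**IOP.** SAP Sections 3.2 and 15.5 schedule it at Visits 1 and 3, with a possible reading at early termination. Protocol Section 8.4.2 lists it among the evaluations that may be done at an unscheduled visit: "These visits may be performed in order to ensure subject safety".

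**The concern.** Because exclusion 9 needs both conditions, a user of pressure-lowering drops who is judged able to stop is not caught by it. Such a subject would stop on Day 1, could not resume without departing from the protocol, and would have no scheduled pressure reading until the exit visit. What is at stake is the safety of a person who gives up a pressure treatment for a short dry-eye study. A secondary question is whether the change in IOP from Visit 1 to Visit 3 would partly reflect withdrawal of the old drug, since the baseline could be read only hours after its last dose.

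**Working it through.** **1. Which rules reach a glaucoma-drop user**

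| Rule | Applies? | Effect |
|---|---|---|
| Exclusion 9 | Yes | Bars only if the drug cannot be discontinued |
| Exclusion 4 | Yes | No drops within 2 hours of Visit 1 |
| Exclusion 6 | No | Names cyclosporine and lifitegrast only |
| Exclusion 15 | At the investigator's judgment | May bar; does not have to |
| Section 8.1.3 | Refers back to Section 5.4 | Adds no interval |

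**2. Interval between scheduled IOP readings**

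Inputs: Visit 1 is Day 1 and there is no Day 0 (SAP Section 3.1); Visit 2 is Day 8 ± 1; Visit 3 is Day 29 ± 2. Elapsed days = study day − 1.

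- Nominal Visit 3: 29 − 1 = 28 days, which reproduces the 28-day treatment period in the synopsis.
- Visit 3 window: 27 − 1 = 26 to 31 − 1 = 30 days.
- Visit 2 window: 7 − 1 = 6 to 9 − 1 = 8 days, with no IOP scheduled.

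Some lines of the Visit 2 list in Protocol Section 8.3.1 are redacted. SAP Section 15.5 names the IOP visits, so a Visit 2 reading is not hidden there.

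**3. How many subjects (assumed)**

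The documents give no prevalence. If a proportion p of enrolled subjects were such users, the chance of at least one among 45 would be 1 − (1 − p)^45 and the expected number 45p.

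| Assumed p | Chance of at least one | Expected number |
|---|---|---|
| 0.5% | 20% | 0.2 |
| 1% | 36% | 0.45 |
| 2% | 60% | 0.9 |
| 5% | 90% | 2.25 |

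These figures only restate the assumption, and refusals under exclusion 15 could bring the number to zero.

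**4. Effect on the IOP summaries (assumed)**

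Take an assumed withdrawal rise of 3 to 7 mmHg in one subject.

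- Shift of an arm mean: 3/15 = 0.20 to 7/15 = 0.47 mmHg.
- Shift of the mean over all 45: 3/45 = 0.07 to 7/45 = 0.16 mmHg.
- Standard error of an arm mean, for an assumed SD of 2 to 4 mmHg: 2/√15 = 0.52 to 4/√15 = 1.03 mmHg.
- Ratio of shift to standard error: 0.20/1.03 = 0.19 up to (7/15)/(2/√15) = 0.90.

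Even the most unfavorable combination is below one standard error.

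**The case against.** **'Cannot' need not mean 'will not'.** A reader might infer that exclusion 9 admits anyone who agrees to stop. The text does not settle that. Exclusions 12 and 19 refer to unwillingness where willingness is meant, so 'cannot' may well mean medically unable, and a patient who needs pressure treatment would then be excluded. This stands. The gap that remains concerns users judged able to stop, and the criterion does not say who makes that judgment or how.

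**The investigator is not blind to the problem.** Medication history, IOP and fundoscopy all come before the second qualification review at Visit 1, and SAP Section 15.4 includes the optic nerve in the fundus examination. Exclusion 15 names both risk and confounding. These are real safeguards. However, an IOP read on residual drug may look normal, and refusal remains a matter of judgment.

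**The subject need not stay off treatment unwatched.** A reader might infer a subject untreated and unmonitored for the whole trial. That is too strong. Visit 2 has a medication update, an adverse event query, visual acuity and slit lamp. Sections 5.5 and 8.6.2 allow withdrawal on safety or medical grounds, and early termination calls for the Visit 3 safety evaluations, which include IOP. An unscheduled visit can include it too. Still, the Visit 2 checks do not measure pressure, and the routes that do are optional or follow an event. Stopping a pressure drug triggers none of them.

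**Conclusion.** The point holds as a modest one about subject protection. The text permits a glaucoma-drop user judged able to discontinue to stop at Visit 1, with a 2-hour washout and the next scheduled IOP reading 26 to 30 days later. That interval follows from the documents alone. The number of subjects affected does not: it is unknown and may be zero.

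A reader might also infer that the IOP safety results would be distorted. The documents do not support this. IOP is summarized descriptively, randomization leaves between-arm comparisons unbiased in expectation, and under the assumed values one subject moves an arm mean by less than one standard error. The minimum and maximum required by SAP Section 8.4 and the planned IOP and ocular history listings would help to trace an unusual value. No change to the SAP is needed. The change is worth making because it is cheap and replaces discretion with a clear rule. Its priority is low.

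**What to change.** In Protocol Section 5.4 and the synopsis:

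- Delete the parenthesis naming glaucoma medication from exclusion 9.
- Add a separate exclusion: 'Be currently using topical IOP-lowering medication, or have used it within 30 days of Visit 1.'

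The 30 days matches exclusions 16 and 18; the exact window is a clinical choice. The documents do not show that it is long enough for every pressure-lowering drug.

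**Alternatives.** Clarifying exclusion 9 to read 'cannot safely discontinue in the treating physician's judgment' would resolve the ambiguity but still let some subjects stop treatment for the study. Adding IOP at Visit 2 would bring the first check forward to 6 to 8 days, with the subject still off treatment. A washout before Visit 1 would lengthen the time off treatment and, under Section 8.1.2, need an earlier consent visit.

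**Cost.** One edited and one added line, with IRB approval of the amendment if the protocol is already approved. No visit, procedure or analysis is added. If an assumed 1% to 5% of screened subjects were newly excluded, keeping 45 enrolled would take 60/(1 − p) − 60 extra screens: 0.6 at 1% and 3.2 at 5%. The population becomes slightly narrower, and it also loses people who stopped such drops within 30 days for reasons unrelated to the trial.
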